## **4.1 Randomisation**

Before randomisation (Day 1/Visit 1/Week 0), subjects will be assessed to ensure that they have signed the ICF and meet eligibility criteria. Once the subject is randomised, relevant data must be captured in the appropriate LTE system. Events that occur prior to randomisation in the LTE study should be reported in Studies D3461C00004 or D3461C00005. Subjects who do not sign the ICF and/or who do not meet the eligibility criteria must not be randomised into the LTE study.

The Week 52 assessments of the Phase 3 Studies D3461C00004 or D3461C00005 will serve as Day 1/Visit 1/Week 0 assessments of the LTE study; additional procedures that are part of the LTE study will also be performed. If Day 1/Visit 1/Week 0 occurs more than 30 days after the Week 52 final visit of the Phase 3 Studies D3461C00004 or D3461C00005, the PRA Medical Monitor must be contacted. In case the Day 1/Visit 1/Week 0 occurs >60 days after the Week 52 final visit of the pivotal studies, additional safety laboratory tests, eg, haematology, liver function tests, and serum creatinine, might be required as judged by the PRA/AZ medical monitor. The rationale for delayed start, date of last dose of study drug, and subject compliance in the prior study will be reviewed. In addition, all procedures for Day 1/Visit 1/Week 0 must be completed.

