### 3. PRIMARY AND SECONDARY VARIABLES

If not stated otherwise, not only data collected during the LTE study but also data collected in the Phase 3 feeder Studies D3461C00004 and D3461C00005 will be considered. If not stated otherwise, all references to Day 1 and date of first dose of investigational product, respectively, refer to the respective day in the Phase 3 feeder studies. The date of last dose of investigational product refers to the last dose during the LTE study for subjects who started the LTE study and to the last dose in the Phase 3 feeder studies for subjects not continuing in the LTE study.

Baseline is defined as baseline of the Phase 3 feeder studies, i.e., the last non-missing measurement prior to dose administration on Day 1. If the Day 1 value is missing or is invalid or is collected after administration of investigational product, the latest assessment prior to dose administration on Day 1 will serve as baseline.

[REDACTED]

[REDACTED]

If not stated otherwise, change from baseline will be calculated as value at the respective post-baseline time point minus value at baseline.

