If an AE has a missing onset date, then unless the stop date of the AE indicates otherwise, it will be assigned to the “Year 1” time interval. Similarly, if an AE has a partial onset date, then unless the partial onset date or the stop date indicates otherwise, it will be assigned to the earliest time interval given the available date information. If the missing or partial start date does not allow an assignment of the event as during the Phase 3 feeder studies or the LTE study, the AE will be assigned to “Year 1” if documented in one of the Phase 3 feeder studies or to “Year 2” if documented in the LTE.

The event rate per 100 subject years is defined as the number of subjects with an event divided by the sum of exposure time in days in the respective time period for all subjects in the analysis set multiplied by 365.25 days/year multiplied by 100. The exposure in a time period for each subject will be calculated as end of period – start of period + 1 (e.g., as the earlier of either (date of last dose of investigational product + 84 days, or date of study discontinuation) - date of first dose of investigational product + 1 day for the summary of all AEs during treatment and follow-up; for AEs during treatment, the same definition will apply, with the exception of last dose of investigational product + 28 days will be used). For analyses based on LTE data only (e.g. AE rates for subjects switching from Placebo to 300 mg anifrolumab in the “All Anifrolumab” treatment group), the first administration of investigational product during the LTE will be considered as the start of the overall period. For analyses based on feeder study data only (e.g. AE rates for subjects switching from Placebo to 300 mg anifrolumab in the “All Randomised Placebo” treatment group), the end of the overall period will be defined as the first administration of investigational product in the LTE -1 day. If a subject discontinued during a period or had the last follow-up visit earlier than expected, the date of study discontinuation/end of study will be used as end of the respective period.

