For AESIs, SAEs, and COVID-19 related analyses of AEs, additional analyses based on an alternative event rate per 100 subject years will be derived as the number of subjects with the respective AE divided by the sum of time at risk in days for all subjects in the analysis set multiplied by 36,525. The time at risk is defined as time (including start and end date) from start of period (e.g., date of first administration of investigational product for all AEs) to the date of first event, death, withdrawal of consent, or end of period, whatever comes first. The same considerations for analyses based on LTE/feeder phase 3 data only as defined above will apply for alternative event rates.

The time to first onset of a specific AESI category will be derived as date of first onset of any AE in the respective category – date of first administration of investigational product + 1. For time to event analyses based on LTE data only (e.g. for subjects switching from Placebo to 300 mg anifrolumab in the “All Anifrolumab” treatment group), the first administration of investigational product during the LTE will be used in the above. AEs with an onset date before the date of first administration of investigational product and AEs with an onset after 84 days after the date of last administration of investigational product will not be considered for the time to first onset of AESI. If a subject has no AESI in a specific category, the time to first onset will be censored at the date of last administration of investigational product + 84 days. For time to event analyses based on feeder study data only (e.g. for subjects switching from Placebo to 300 mg anifrolumab in the “All Randomised Placebo” treatment group), the

minimum of last administration of investigational product in the feeder study +84 days and first administration of investigational product in the LTE -1 day will be used in the above. If a subject discontinued the study or had the last follow-up visit earlier than expected, the date of study discontinuation/end of study will be used as the censoring date.

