**Table 2 Visit windows**

Adjusted Defined Windows Visit	Scheduled Study Day	Maximum Windows
Baseline / Day 1	1	Study Day $\leq 1$
Week 24	169	$155 \leq \text{Study Day} \leq 182$
Week 52	365	$351 \leq \text{Study Day} \leq 378$ and LTE Study Day 1
Gap a	N/A	$379 \leq \text{Study Day} \leq \text{LTE Study Day 1}$
Week 56	29 in LTE study	$2 \leq \text{LTE Study Day} \leq 42$
Week 60	57 in LTE study	$43 \leq \text{LTE Study Day} \leq 70$
Week 64	85 in LTE study	$71 \leq \text{LTE Study Days} \leq 98$
...	...	...
Continue in 4-week intervals	Continue in 28-day intervals	Continue in 28-day intervals
...	...	...
Variables to be assessed/measured during follow-up		
Week 208	1092 in LTE study	$1079 \leq \text{LTE Study Days} \leq 1106$
Week 212 (8 weeks post-final dose)	1120 in LTE study	$1107 \leq \text{LTE Study Days} \leq 1134$
Week 216 (12 weeks post-final dose)	1148 in LTE study	$1135 \leq \text{LTE Study Days}$
Variables not to be assessed/measured during follow-up		
Week 208	1092 in LTE study	$1079 \leq \text{LTE Study Day}$

a. This visit window covers longer than expected gaps between the feeder study and the first dose date in the LTE. This visit window will only be used in listings.

For assignment of data to time points using the visit windows, study day will be defined as (Date of assessment – date of first administration of investigational product) +1. Using this definition, the day of first dose of investigational product will be Day 1 and the scheduled visit date of Week 24 will be study day 169 (=168+1), for example. Data captured in the Phase 3 feeder study falling in a visit window after Week 52 [REDACTED] captured in the Phase 3 feeder study falling in Week 52 visit window will not be considered for by-visit summaries. LTE Study Day is defined accordingly as (Date of assessment – date of first administration of investigational product in LTE study) +1. Data assessed at LTE Study Day 1 will be assigned to Week 52 visit window. Data captured in the LTE study after LTE Study Day 1 falling into a visit window before Week 56 will not be considered for by-visit summaries.

If multiple readings are recorded within a single visit window, the following rules will be followed:

- If there are 2 or more observations within the same visit window, then the non-missing one closest to the scheduled visit will be used in the analysis.

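### Placebo subjects who switch to anifrolumab have three different ends of placebo follow-up (AE rates, AESI Kaplan-Meier, flare rates), and any gap before the LTE is labelled as treatment time

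*SAP*

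**What the plan says.** **Which last dose counts.** SAP section 3 states: "The date of last dose of investigational product refers to the last dose during the LTE study for subjects who started the LTE study". SAP 3.1.1 then sorts AEs by time since that dose: *during treatment* up to 28 days after it, *follow-up* from then to 84 days.

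**Rates, general rule.** The denominator starts at the first dose and ends at the earlier of "date of last dose of investigational product + 84 days, or date of study discontinuation". For *during treatment* it is the same, "with the exception of last dose of investigational product + 28 days will be used".

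**Rates, placebo switchers in Randomised Placebo.** These are analysed on feeder data only, and "the end of the overall period will be defined as the first administration of investigational product in the LTE -1 day". For the time-at-risk rates of AESIs and SAEs: "The same considerations for analyses based on LTE/feeder phase 3 data only as defined above will apply for alternative event rates". The numerator matches: only AEs from the first LTE dose onward are removed.

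**Kaplan-Meier time to first AESI, same subjects.** The end is the "minimum of last administration of investigational product in the feeder study +84 days and first administration of investigational product in the LTE -1 day".

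**Flare rate, same subjects (SAP 3.1.5).** The same form, but with 28 days in place of 84.

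**Length of the gap.** The LTE should start on the day of feeder Week 52. A delay of up to 30 days is allowed, and a longer one after contact with the medical monitor. Protocol 4.1 adds a provision for still later starts: "In case the Day 1/Visit 1/Week 0 occurs >60 days after the Week 52 final visit of the pivotal studies". No maximum is given. SAP Table 2 has a Gap row, used in listings only, with the footnote "This visit window covers longer than expected gaps between the feeder study and the first dose date in the LTE".

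**Principle.** SAP 4.2 includes data whether or not treatment was stopped early or delayed.

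**The concern.** AESI and SAE rates are the primary outcome, and the Kaplan-Meier plots show the same AESIs over time. A reader will expect both to rest on the same follow-up and the same events. For a switcher with a long gap they do not: an AESI late in the gap counts in the rate and is dropped from the plot. The flare rate uses a third end.

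The second issue is labelling. Because the last dose is the last LTE dose for every entrant, a day or event in the gap counts as *during treatment* however long ago the last feeder dose was. The same event in a subject who never enters the LTE would be *follow-up* or out of window, so the label depends on something that happens later. This touches the AE and SAE tables that SAP 4.2.1.1 splits into treatment and follow-up, for which a rate is planned only during treatment. With rare AESIs, one relabelled event can matter more than the change in the denominator.

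**Working it through.** **1. The plan's own figure.** SAP 4.1.3 gives an exact Poisson 95% CI of 4.56 to 19.03 per 1000 subject-years for a rate of 10 per 1000 and 893 subject-years. With e = 8.93 events and T = 893: χ²(0.025; 2e)/(2T) = 4.556 and χ²(0.975; 2e + 2)/(2T) = 19.029 per 1000. It reproduces and serves below as a yardstick. The 893, 517 and 1343 subject-years cannot be rebuilt, because feeder-arm sizes are not given.

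**2. End dates for a switcher.** SAP 4.2.3.1 puts the last feeder dose at Week 48 (Visit 13). Count days from that dose. Week 52 is day 28, and an LTE start d days after Week 52 is day 28 + d.

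- Rate end: 27 + d
- Kaplan-Meier end: min(84, 27 + d)
- Flare end: min(28, 27 + d)

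| d (days after Week 52) | Rate end | Kaplan-Meier end | Flare end | Rate − Kaplan-Meier | Rate − flare |
|---|---|---|---|---|---|
| 0 | 27 | 27 | 27 | 0 | 0 |
| 30 | 57 | 57 | 28 | 0 | 29 |
| 57 | 84 | 84 | 28 | 0 | 56 |
| 58 | 85 | 84 | 28 | 1 | 57 |
| 60 | 87 | 84 | 28 | 3 | 59 |
| 90 | 117 | 84 | 28 | 33 | 89 |
| 120 | 147 | 84 | 28 | 63 | 119 |

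The rate and Kaplan-Meier ends differ when 27 + d > 84, so from d = 58. If the Week 48 dose was missed and the last dose was at Week 44 (four-weekly dosing assumed), Week 52 is day 56, the rate end is 55 + d, and the ends differ from d = 30. The *during treatment* rate and flare ends differ when 27 + d > 28, so from d = 2.

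**3. Subject-years in the rates but not in the Kaplan-Meier analysis.** Approximately 575 entrants at 4:1 give 575/5 = 115 on placebo and, with 1:1 re-randomisation, about 115 switchers. The excess is 115 × share × (d − 57)/365.25.

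- 10% delayed 90 days: 11.5 × 33/365.25 = 1.0 subject-year, 0.2% of 517.
- All delayed 90 days: 115 × 33/365.25 = 10.4, 2.0% of 517.
- All delayed 60 days: 115 × 3/365.25 = 0.9, 0.2% of 517.

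**4. The label for one event in the gap.**

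| Days after last feeder dose | Never enters the LTE | Enters the LTE after the event |
|---|---|---|
| 60 | follow-up | during treatment |
| 100 | in neither category | during treatment |

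**5. Gap time in the *during treatment* rate of Randomised Anifrolumab 300 mg.** The entrants already on anifrolumab number about 575 − 115 − 115 = 345 over both doses, an upper bound for the 300 mg group; 150 is an assumed low figure. Days beyond 28 are d − 1 per delayed subject.

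- 10% delayed 30 days: 15 × 29/365.25 = 1.2 to 34.5 × 29/365.25 = 2.7 subject-years, 0.1% to 0.3% of 893.
- All delayed 30 days: 150 × 29/365.25 = 11.9 to 345 × 29/365.25 = 27.4, 1.3% to 3.1% of 893.

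**6. Direction.** Let the gap be a share g of the 893 subject-years and r the ratio of gap risk to on-drug risk. An on-drug rate of 10 per 1000 is then observed as 10 × (1 − g + g·r). In the extreme case above g = 27.4/893 = 0.0307, which gives 9.69 for r = 0, 10.00 for r = 1 and 10.08 for r = 1.25. All lie far inside 4.56 to 19.03.

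**The case against.** Much of the case on the other side stands.

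- **A reader might infer that off-drug time dilutes the anifrolumab rates.** The documents do not show this. Gap events are to be recorded in the feeder study and are counted, and gap time enters the placebo denominator too. The direction depends on an unknown risk in the gap (step 6). The uncapped sentence itself governs placebo switchers, not anifrolumab time.
- **A reader might infer that the rates and Kaplan-Meier plots also disagree in the anifrolumab groups.** They do not. For subjects continuing on anifrolumab, both analyses run through the gap; only the label is at issue.
- **Including delayed time is a stated choice.** SAP 4.2 says so, and the uncapped end agrees with the switchers' exposure definition in SAP 3.3.4. This answers any demand to strip gap time from the main rates of continuing subjects. It does not explain three ends for one switcher.
- **Most AE summaries use the 84-day window** (SAP 4.2.1.1). Days 29 to 84 after the last feeder dose are valid time there, so step 5 bears only on the *during treatment* tables.
- **Long gaps may be few.** Starts beyond 30 days need individual review, and the rate and Kaplan-Meier ends agree within that limit unless late feeder doses were missed.
- **The SAP may already close the period.** A sentence in 3.1.1 ends a period at study discontinuation or end of study. It does not say whether a feeder end-of-study date applies to someone who enters the LTE later, so two programmers could read it differently.

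**Conclusion.** The inconsistency is real but narrow. For placebo switchers the SAP sets three ends of placebo follow-up. The rate and Kaplan-Meier ends part from a 58-day delay after Week 52, or about 30 days after a missed Week 48 dose. The *during treatment* rate and flare ends part within the permitted delay. Separately, any gap event in an LTE entrant is labelled *during treatment*, whatever the time since the last feeder dose.

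The numerical effect on rates is probably small: about 0.2% of 517 subject-years if 10% of switchers start 90 days late, and 2.0% if all do. The direction is unknown, so the point does not support a claim of bias in favour of anifrolumab. It is worth correcting because it concerns the primary AESI and SAE rates and the correction uses a rule that the SAP already contains.

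The sizes rest on assumptions: the share delayed, the length of delay, about 115 switchers, and 150 to 345 entrants in the 300 mg group. The documents do not give the distribution of delays.

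**What to change.** 1. **Switchers, denominator (SAP 3.1.1).** Replace the uncapped end with the minimum rule already used for Kaplan-Meier and flares. For treatment and follow-up: the earlier of last feeder dose + 84 days and first LTE dose − 1 day. For during treatment: the same with + 28 days. Apply it to the standard and the alternative rates. The first then matches the Kaplan-Meier end and the second the flare end.
2. **Switchers, numerator.** Apply the same limits to the AE categories, and list any later gap events so that none is lost.
3. **Subjects continuing on anifrolumab or placebo.** Keep the main all-data rates. Add a sensitivity *during treatment* rate that leaves out gap days and gap events more than 28 days after the last feeder dose.
4. **Reporting.** Show the distribution of the feeder-to-LTE gap by treatment group.
5. **Clarification.** State whether a feeder end-of-study date closes the period for a delayed entrant. Footnote that the switchers' exposure in SAP 3.3.4 keeps the uncapped end, or align it.

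The cost is a few sentences, little code, one sensitivity rate and one descriptive table. A few subject-years and events in long gaps move from the switchers' rates to a listing.
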